10.3.2 Permanent treatment discontinuation with investigational medicinal product(s)

Permanent treatment discontinuation is any treatment discontinuation associated with the definitive decision from the Investigator or the patient not to re-expose the patient to the IMP at any time.

10.3.3 List of criteria for permanent treatment discontinuation

The patients may withdraw from treatment with the IMP if they decide to do so, at any time and irrespective of the reason, or this may be the Investigator's decision. All efforts should be made to document the reasons for treatment discontinuation and this should be documented in the e-CRF.

IMP will be permanently discontinued in case of the following events (refer to [Section 10.6](#) for details). The list is not intended to be exhaustive:

- [REDACTED]
- Symptoms of severe hypersensitivity or anaphylactic reactions (see [APPENDIX D](#) for definition)
- Severe skin reactions local to the site of IMP injection (see [APPENDIX E](#))
- Pregnancy
- Any adverse events, per Investigator's judgment, that may jeopardize the patient's safety

- Any laboratory abnormalities according to [APPENDIX F](#)
- All efforts should be made to reassess in a clinically relevant timeframe (using either local or central lab) the clinical significance of lab abnormalities and corrective actions before making a decision of permanent discontinuation of the IMP for the concerned patient.
- Any code breaking requested by the Investigator will lead to permanent treatment discontinuation
- At the specific request of the Sponsor

Any abnormal ECG parameter will be immediately rechecked for confirmation before making a decision of permanent discontinuation of the IMP for the concerned patient.

10.3.4 Handling of patients after permanent treatment discontinuation

Patients will be followed-up according to the study procedures as specified in this protocol up to the scheduled date of study completion, or up to recovery or stabilization of any AE to be followed-up as specified in this protocol, whichever comes last.

If possible, and after the permanent discontinuation of treatment, the patients will be assessed using the procedure normally planned for the last dosing day with the IMP (End of treatment visit/Visit 9) and then will be asked to come to the scheduled on site visits for safety monitoring and respiratory function assessment (FVC and DLCO).

All cases of permanent treatment discontinuation should be recorded by the Investigator in the appropriate pages of the e-CRF when considered as confirmed.

10.3.5 Procedure and consequence for patient withdrawal from study

The patients may withdraw from the study before study completion if they decide to do so, at any time and irrespective of the reason.

If possible, the patients are assessed using the procedure normally planned for the end-of-study visit (Visit 10). Then, patients will receive a phone call from Investigators at week 52 for vital status assessment.

For patients who fail to return to the site, the Investigator should make the best effort to contact the patient (e.g. contacting patient's family or private physician, reviewing available registries or health care databases), and to determine his/her health status, including at least his/her vital status. Attempts to contact such patients must be documented in the patient's records (e.g. times and dates of attempted telephone contact, receipt for sending a registered letter).

The statistical analysis plan will specify how these patients lost to follow-up for their primary endpoints will be considered.

Patients who have withdrawn from the study cannot be re-randomized (treated) in the study. Their inclusion and treatment numbers must not be reused.

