
4.2 RATIONALE

4.2.1 Study design

DRI11772 study will consist of the evaluation of the efficacy and safety of 2 dose levels/regimens of SAR156597 administered subcutaneously over a 52-week treatment period and, the determination of the optimal dose level/regimen for the treatment of patients with IPF.

It will be a multinational, randomized, double-blind, placebo-controlled, 3-parallel group study conducted in out-patients suffering from IPF according to the American Thoracic Society/ European Respiratory Society/ Japanese Respiratory Society/ Latin American Thoracic Association (ATS/ERS/JRS/ALAT) guideline criteria and confirmed by a multidisciplinary panel of experts in IPF.

Patients who discontinue treatment during the study will be followed for the full planned 52 week duration of the study in order to ensure the collection of efficacy outcomes on all randomized patients and minimize the potential for bias in analyses due to missing data.

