7.2 EXCLUSION CRITERIA

E 01. Age \leq 40 years.

E 02. IPF disease diagnosis $>$ 5 years.

E 03. Forced vital capacity (FVC) $<$ 40% of predicted value.

E 04. Carbon monoxide diffusing lung capacity (DLCO) corrected for hemoglobin $<$ 30% of predicted value.

E 05. Severe chronic obstructive bronchitis as characterized by FEV1/FVC $<$ 0.70.

- E 06. Need for 24 hrs of oxygen therapy or oxygen saturation <88% after 10 minutes breathing ambient air at rest.
- E 07. Known diagnosis of significant respiratory disorders (e.g. asthma, tuberculosis, sarcoidosis, aspergillosis, or cystic fibrosis) other than IPF.
- E 08. Pulmonary artery hypertension requiring a specific treatment.
- E 09. Currently listed and/or anticipated to be listed for lung transplantation within the next 6 months (on an active list).
- E 10. History of vasculitis or connective tissue disorders or ANCA positive.
- E 11. Known HIV or chronic viral hepatitis.
- E 12. Exclusion related to tuberculosis (TB):
- Active tuberculosis (according to WHO guidelines (25) or a history of incompletely treated tuberculosis
 - Incompletely treated latent tuberculosis (according to WHO guidelines)
 - Positive or confirmed indeterminate (2 consecutive tests) QuantiFERON-TB Gold® test at screening (regardless of prior treatment status)
- E 13. Evidence of any clinically significant, severe or unstable, acute or chronically progressive medical (other than IPF) or surgical disorder, or any condition that may affect patient safety in the judgment of the investigator.
- E 14. Acute myocardial infarction within 6 months prior to screening.
- E 15. Clinically significant abnormal electrocardiogram (ECG) at screening that may affect the conduct of the study in the judgement of the investigator.
- E 16. Clinically significant laboratory tests at screening:
- Alanine transaminase (ALT) or aspartate transaminase (AST) >2 times upper limit of normal range (ULN)
 - Hemoglobin <11 g/100 mL for male and <10 g/100 mL for female
 - Neutrophils <1500/mm³ (except <1000/mm³ for those of African descent)
 - Platelets <100 000/mm³
 - Creatinine ≥150 µmol/L
- E 17. Current history of substance and/or alcohol abuse.

E 18. Females who are lactating or who are pregnant.

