10.4.4 Instructions for reporting serious adverse events

In the case of occurrence of a SAE, the Investigator must immediately:

- ENTER (within 24 hours) the information related to the SAE in the appropriate screens of the e-CRF; the system will automatically send a notification to the monitoring team after approval of the Investigator within the e-CRF or after a standard delay.
- SEND (preferably by fax or e-mail) a photocopy of all examinations carried out and the dates on which these examinations were performed, to the representative of the monitoring team whose name, fax number, and email address appear on the clinical trial protocol. Care should be taken to ensure that the patient's identity is protected and the patient's identifiers in the clinical trial are properly mentioned on any copy of a source document provided to the Sponsor. For laboratory results, include the laboratory normal ranges.
- All further data updates should be recorded in the e-CRF as appropriate, and further documentation as well as additional information (for laboratory data, concomitant medications, patient status, etc) should be sent (by fax or e-mail) to the monitoring team within 24 hours of knowledge of the SAE. In addition, every effort should be made to further document any SAE that is fatal or life threatening within a week (7 days) of the initial notification.
- A back-up plan (using a paper CRF process) is available and should be used when the e-CRF system does not work.

Any SAE brought to the attention of the Investigator at any time after the end of the study for the patient and considered by him/her to be caused by the IMP with a reasonable possibility, should be reported to the monitoring team.

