##### *2.1.3.2.2 Disease progression endpoint*

Disease progression is defined as time from randomization to the first occurrence of any of the following events:

- decrease in absolute % predicted FVC $\geq$ 10% (as in [Section 2.1.3.1](#))
- decrease in absolute % predicted DLCO $\geq$ 15% (as in [Section 2.4.4.2.3](#))
- lung transplant (recorded on the dedicated e-CRF page during the study)
- death (recorded on the dedicated e-CRF page during the study)

Disease progression will be analyzed as a time-to-event variable: event date – randomization date + 1 day where the event date is described in [Table 2](#).

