- ii. Other patients (patients in active arm and not taking treatment at 52 weeks; or patients in placebo arm): Missing values at 52 weeks will be imputed using a model estimated from the subset of patients in the placebo arm who completed the 52-week treatment period and with a week 52 value. The imputation model will be based on a Mixed Model with Repeated Measures (MMRM) with fixed categorical effect of stratification factor (with/without Background Therapy) and repeated categorical effect for time point (baseline, week 12, week 24, week 36, week 52). Parameters will be estimated with the Newton-Raphson algorithm, an unstructured covariance matrix will model the within-patient errors, and the denominator degrees of freedom will be estimated using

- Satterthwaite's approximation. Missing values at 52 weeks will be imputed using the empirical best linear unbiased prediction (EBLUP).
- iii. When running the imputation model, if the predicted absolute change from baseline calculated from the predicted week 52 value is greater than zero (increases above baseline), it will be set to zero.
  - iv. The non-monotone missing patterns with a week 52 value available will not be imputed.
- b) Week 52 missing values due to lung transplant:
    - i. Any % predicted FVC value assessed after a lung transplant will be considered as missing.
    - ii. No imputation of a week 52 value for % predicted FVC. In step 2, patients will be ranked worse than missing data due to reasons other than death or lung transplant.
  - c) Week 52 missing values due to death :
    - i. No imputation of a week 52 value for % predicted FVC. In step 2, patients will be ranked worse than missing data due to lung transplant.
2. Rank ANCOVA
- a) Ranking within each stratum of the stratification factor (with/without Background Therapy)
    - i. Death: Missing data due to death will be ranked based on a time-to-death, with shortest time until death as the worst (lowest) rank (from 1 to  $n_{\text{stratum,death}}$ ).
    - ii. Lung transplant: Missing data due to lung transplant will be ranked based on a time-to-lung transplant, with shortest time until lung transplant as the worst (lowest) rank (from  $n_{\text{stratum,death}}+1$  to  $n_{\text{stratum,death}}+n_{\text{stratum,lungtransplant}}$ ). So, missing data due to lung transplant will be less penalized than deaths.

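### Transplant status need not be collected after study withdrawal, so a transplanted withdrawal can be imputed in the primary analysis instead of ranked just above the deaths

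*Protocol*

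**What the plan says.** **After study withdrawal.** Protocol 10.3.5 asks that, if possible, "the patients are assessed using the procedure normally planned for the end-of-study visit (Visit 10"). After that, "patients will receive a phone call from Investigators at week 52 for vital status assessment". For patients who fail to return, the investigator makes best efforts through family, physician, registries or databases "to determine his/her health status, including at least his/her vital status". Transplant is not named in either route.

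**After stopping treatment only.** Protocol 4.2.1 is different: "Patients who discontinue treatment during the study will be followed for the full planned 52 week duration of the study". These patients keep their visits and are not part of this point.

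**Source of transplant data.** SAP 2.1.3.2.2 lists as a progression event "lung transplant (recorded on the dedicated e-CRF page during the study"). Protocol 10.4.4 addresses "Any SAE brought to the attention of the Investigator at any time after the end of the study for the patient", but makes it reportable only where the investigator considers it caused by the study drug.

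**Use in the analysis.** SAP 2.4.4.1 sorts missing Week 52 values by reason. Deaths take the lowest ranks. Next, "Missing data due to lung transplant will be ranked based on a time-to-lung transplant", above deaths and below everyone else. All other missing values are imputed by a mixed model fitted to treatment completers with a Week 52 value. The placebo-completer model serves placebo patients and active patients who are off treatment. Predicted gains over baseline are set to zero.

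**The concern.** The ranking presumes that the reason for a missing Week 52 value is known, and the required follow-up of withdrawals supplies that for death but not for transplant. Consider two patients who withdraw at Week 30. One dies at Week 45; the call finds this and the patient takes one of the worst ranks. The other is transplanted at Week 45, and a call confined to vital status finds a living patient. That patient then counts as missing for other reasons and is imputed.

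Transplants within the year are possible. Exclusion E 09 in Protocol 7.2 covers patients "Currently listed and/or anticipated to be listed for lung transplantation within the next 6 months", which lowers the number but does not rule out later ones.

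Capture of a near-worst outcome would then depend on whether the patient stayed in the study. If withdrawal before transplant differs by arm, the comparison is biased. The same gap reaches disease progression, where transplant is a component, and SAP Table 3, which counts transplant as an event in the all-cause mortality analysis. The two sensitivity analyses do not test it: the first uses the same reason classes, and the second uses on-treatment data without imputation.

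**Working it through.** **1. The plan's own figure.** Inputs from Protocol 11.1: difference 5, SD 12, two-sided 5%, power 80%.

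n = 2(1.960 + 0.842)² × 12² / 5² = 2 × 7.849 × 5.76 = 90.4, so 91 per arm. The t-test version gives 91.4, so 92. The stated 92 reproduces. The documents give no figure for transplants or withdrawals, so what follows rests on assumptions.

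**2. Who is affected.** A patient's primary rank changes only if all of these hold:
- withdrew from the study, not just from treatment;
- transplanted after withdrawal, by Day 375;
- alive at the call (a death is ranked as a death);
- no valid FVC in the Week 52 window, study days 309 to 406 (SAP Table 6); a withdrawal-visit FVC from Day 309 would count as observed;
- baseline and at least one post-baseline FVC, since SAP 1.5 indicates that a change cannot otherwise be imputed.

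A study withdrawal is off treatment, so the placebo-completer model would normally apply in both arms.

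**3. Shift per missed transplant.** Assume 100 per arm, roughly uniform standardized ranks (variance 1/12), no stratification, and a recorded transplant at rank about 0.02.

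SE of the mean-rank difference = √(2 / (12 × 100)) = 0.0408.

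Shift = (imputed rank − 0.02) / 100, divided by 0.0408:

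| Assumed imputed rank | Shift in mean rank | In SE |
|---|---|---|
| 0.10 | 0.0008 | 0.02 |
| 0.20 | 0.0018 | 0.04 |
| 0.40 | 0.0038 | 0.09 |
| 0.50 | 0.0048 | 0.12 |

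Three misses in one arm and none in the other give three times this, about 0.06 to 0.35 SE.

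**4. Effect on power.** An unstratified simulation of the rank ANCOVA was run with 100 per arm and 4,000 runs per scenario. The 5-point effect and SD of 12 come from the plan. Assumed, not from the documents: placebo mean change −9, five deaths per arm, and imputed values drawn around −9 with SD 6 and capped at zero. That imputed value is close to an average placebo patient, so these results sit toward the upper end. With no transplants, power is 74.0%.

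| Transplants, placebo / active | Recorded | Imputed | Mean change in z |
|---|---|---|---|
| 1 / 1 | 73.0% | 73.8% | +0.04 |
| 2 / 2 | 71.3% | 73.5% | +0.07 |
| 3 / 0 | 83.3% | 75.4% | −0.25 |
| 5 / 0 | 89.0% | 76.6% | −0.40 |
| 0 / 3 | 58.2% | 72.4% | +0.35 |
| 0 / 5 | 44.9% | 69.3% | +0.58 |

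The Monte Carlo standard error of one percentage is about √(0.74 × 0.26 / 4000) = 0.7 points.

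With no FVC effect and transplants on active only, a false significant benefit occurs in 0.6% of runs if recorded and 1.6% if imputed (three transplants), and in 0.2% and 1.7% (five). All are below the nominal 2.5%.

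**The case against.** The strongest reply is that the gap is narrow and the plan partly covers it. Most of this stands and limits the point.

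- **A reader might infer that such transplants go unrecorded.** The text does not say that only vital status is asked. Tracing of non-returners aims at health status and could find a transplant, and SAP 2.2 refers to a vital-status form whose fields are not shown. The supportable statement is that a transplant need not be recorded.
- **A reader might take the SAP's in-study wording to shut out later transplants.** SAP 2.1.3.2.2 uses the same wording for death, so it cannot exclude one and admit the other. Tables 2 and 3 and steps 1b and 2a would already handle a transplant learned at the call.
- **A reader might think the patient is treated as an average completer.** The model has an unstructured within-patient covariance, so the prediction uses the patient's own earlier FVC. Someone declining steeply may get a low value, hence the lower end of 0.10 for the assumed rank.
- **A reader might count every missed transplant as a lost progression event.** Progression is the first of four events. Such a patient may already have had an FVC or DLCO event, and the withdrawal assessment includes both tests.
- **A reader might suppose that patients leave when transplant work-up starts.** Nothing in the documents supports this. Patients are to be kept in the study as long as possible.

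What the reply does not remove is that the guaranteed minimum on both routes is vital status, and that later serious events are reportable only if attributed to the study drug. No provision requires the transplant status that the ranking uses.

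**Conclusion.** The point holds in a limited form: it is an ascertainment gap with a probably small effect. Following the plan as written can place a transplanted withdrawal among the imputed values instead of just above the deaths. It can also lose an event in the mortality table and, where no FVC or DLCO event came first, in the progression analysis.

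Under assumed imputed ranks of 0.10 to 0.50 and 100 per arm, the shift is about 0.02 to 0.12 SE per missed transplant. One or two misses per arm, in balance, move simulated power by about 1 to 2 points. Changes of roughly 8 to 24 points appear only with three to five misses in one arm and none in the other, and with imputed values near the placebo average.

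A reader might conclude that the gap flatters the drug or inflates the type I error. Neither follows. Missed transplants on active favour the drug and missed transplants on placebo work against it. In the simulated cases without an FVC effect, false benefit stayed below 2.5%.

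**What to change.** In Protocol 10.3.5, change the content of the Week 52 call to vital status and lung transplant status, with the date of any transplant. Set the same minimum for tracing patients who fail to return. Enter the answer on the existing transplant e-CRF page.

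The SAP needs at most one clarifying line in 2.1.3.2.2: deaths and transplants up to Day 375 learned from this contact count as events. Tables 2 and 3 and the ranking steps can stay as they are.

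The cost is one more question in a contact already planned, and its e-CRF entry. Some withdrawn patients may decline to answer, so the gap would shrink but might not close.

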10.4 OBLIGATION OF THE INVESTIGATOR REGARDING SAFETY REPORTING

10.4.1 Definitions of adverse events

10.4.1.1 Adverse event

An **adverse event** (AE) is any untoward medical occurrence in a patient or clinical investigation patient administered a pharmaceutical product and which does not necessarily have to have a causal relationship with this treatment.

Intensity of an AE is defined as:

- Mild: no modification of daily activities and does not require mandatory corrective/symptomatic treatment
- Moderate: hinders normal daily activities and/or requires mandatory corrective/symptomatic treatment
- Severe: prevents daily activities and requires mandatory corrective/symptomatic treatment

10.4.1.2 Serious adverse event

A **serious adverse event** (SAE) is any untoward medical occurrence that at any dose:

- Results in death, or
- Is life-threatening, or
Note: The term “life-threatening” in the definition of “serious” refers to an event in which the patient was at risk of death at the time of the event; it does not refer to an event which hypothetically might have caused death if it were more severe.
- Requires inpatient hospitalization or prolongation of existing hospitalization, or
- Results in persistent or significant disability/incapacity, or
- Is a congenital anomaly/birth defect
- Is a medically important event

Medical and scientific judgment should be exercised in deciding whether expedited reporting is appropriate in other situations, such as important medical events that may not be immediately life-threatening or result in death or hospitalization but may jeopardize the patient or may require medical or surgical intervention (ie, specific measures or corrective treatment) to prevent one of the other outcomes listed in the definition above.

Note: The following list of medically important events is intended to serve as a guideline for determining which condition has to be considered as a medically important event. The list is not intended to be exhaustive:

- Intensive treatment in an emergency room or at home for:
 - Severe hypersensitivity reactions (e.g. anaphylaxis, allergic bronchospasm [see [APPENDIX D](#) for the clinical criteria for diagnosing anaphylaxis])
 - Blood dyscrasias (ie, agranulocytosis, aplastic anemia, bone marrow aplasia, myelodysplasia, pancytopenia, etc),
 - Convulsions (seizures, epilepsy, epileptic fit, absence, etc).
- ALT >3 x ULN + total bilirubin >2 x ULN or asymptomatic ALT increase >10 x ULN. See [APPENDIX F](#)
- Acute exacerbation of IPF
- Suicide attempt or any event suggestive of suicidality
- Syncope, loss of consciousness (except if documented as a consequence of blood sampling)
- Bullous cutaneous eruptions
- Cancers diagnosed during the study or aggravated during the study
- Chronic neurodegenerative diseases (newly diagnosed) or aggravated during the study (only if judged unusual/significant by the Investigators in studies assessing specifically the effect of a study drug on these diseases).
- If any suspected transmission of an infectious agent via a medicinal product (e.g. product contamination).

[figure not shown]
10.4.1.3 Adverse event of special interest

An adverse event of special interest (AESI) is an AE (serious or non-serious) of scientific and medical concern specific to the Sponsor's product or program, for which ongoing monitoring and immediate notification by the Investigator to the Sponsor is required. Such events may require further pre-specified investigation/monitoring in order to characterize and understand them. Adverse events of special interest may be added or removed during a study by protocol amendment.

- Pregnancy of a female subject entered in a study as well as pregnancy occurring in a female partner of a male subject entered in a study with IMP

Pregnancy occurring in a female patient entered in the clinical trial or in a female partner of a male patient entered in the clinical trial. It will be qualified as an SAE only if it fulfills one of the seriousness criteria (see [Section 10.4.1.2](#)).

- In the event of pregnancy in a female participant, IMP should be discontinued.
- Follow-up of the pregnancy in a female participant or in a female partner of a male participant is mandatory until the outcome has been determined.

- Symptomatic overdose (serious or non-serious) with IMP
 - An overdose (accidental or intentional) with the IMP is an event suspected by the Investigator or spontaneously notified by the patient and defined as at least twice the intended dose during an interval of less than 5 days.
Of note, asymptomatic overdose has to be reported as a standard AE.
- Increase in ALT $\geq 3 \times \text{ULN}$ (if baseline ALT $< \text{ULN}$) or $\geq 2 \times$ baseline value (if baseline ALT $\geq \text{ULN}$). See the “Increase in ALT” flowchart in [APPENDIX F](#) of the protocol).
- Other project specific AESI (s):
 - 
 - Anaphylactic reactions or acute allergic reactions that require immediate treatment (refer to [APPENDIX D](#) for definition of Anaphylaxis)
 - Severe injection site reactions (see [APPENDIX E](#))
 - Tuberculosis or initiation of medications for suspected tuberculosis
 - Acute renal failure (see [APPENDIX F](#)).

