8 STUDY TREATMENTS

8.1 INVESTIGATIONAL MEDICINAL PRODUCT(S)

A complete description of the Investigational Medicinal Product (IMP) and its proper handling will be provided in a pharmacy manual.

- Pharmaceutical form
 - SAR156597 solution for injection at 100 mg/mL: SAR156597 is supplied as a sterile freeze-dried powder for solution for injection. Each vial is overfilled with 125 mg of SAR156597 freeze-dried powder, and the final solution for injection is obtained by reconstitution of the entire vial content with 1.1 mL of water for injection, leading to an amount of 125 mg of SAR156597 drug substance in a total volume of 1.25 mL, that is a 100 mg/mL of SAR156597 solution. 1 mL of this 100 mg/mL SAR156597 solution can then be withdrawn for dose administration. 2 drug product vials are thus needed to reach a 200 mg dose.
 - Placebo consists of liquid with the same excipients as those of the reconstituted SAR156597 formulation, filled at nominal volume of 1.5 mL. Two vials are necessary, 1 mL will be taken from each vial to prepare 2 mL syringe.
- Method of preparation

At the study site, reconstitution of the IMP must be done by personnel other than those administering the drug and making clinical observations (e.g. pharmacist) to maintain the treatment blind (Refer to [Section 8.4](#)).

- At patient's home, reconstitution must be done by healthcare professionals (e.g. visiting nurse) out of view of patients and their families/caregivers.
- The IMP should be reconstituted the day of dosing (no more than 3 hours prior to SC injection), at room temperature.
- Dose of drug per administration
 - SAR156597 qw arm: one injection of SAR156597 200 mg administered subcutaneously every week
 - SAR156597 q2w arm: one injection of SAR156597 200mg administered subcutaneously once every 2 weeks alternating with one injection of placebo administered subcutaneously once every 2 weeks
 - Placebo arm: one injection of placebo administered every week

- Route and method of administration

The route and method of administration are subcutaneous in the abdomen. Subcutaneous injection sites should be alternated between the 4 quadrants of the abdomen (avoiding navel and waist areas) so that the same site is not injected for two consecutive weeks. Exact site of each injection will be documented on source document.

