The IMP is administered every 7 days +/- 2 days from initial IMP administration. This is permitted per protocol to accommodate special circumstances, eg. laboratory results pending, ongoing AE, patient scheduling difficulty.

If IMP administration is missed or temporarily discontinued, the initial schedule of injections should be resumed. This does not apply to permanent treatment discontinuation.

On days when the patient has a study visit, the IMP will be administered by the Investigator or delegate after clinic procedures and blood collection.

For doses not administered at the study site, the IMP will be administered by qualified site personnel and /or healthcare professionals (e.g. visiting nurse service).

Patients should be monitored by site personnel/visiting nurse for at least 30 minutes after each administration for potential signs and symptoms that may suggest a hypersensitivity reaction.

[For Czech Republic only per local requirement: Patients should be monitored at the study site by site personnel for a minimum of 2 hours after the first administration of IMP and for a minimum of 1 hour after the next 5 administrations for potential signs and symptoms that may suggest a hypersensitivity reaction. For the subsequent IMP administrations, patients should be monitored by site personnel/visiting nurse for at least 30 minutes after each administration.]

For doses not given at study site, a booklet will be provided to the patient to record information related to the injections; this booklet will be completed by the visiting nurse after each injection and will be kept as source data in the patient's study file. Patients will be instructed to bring the booklet back at the subsequent site visit for Investigator's review.

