10 STUDY PROCEDURES

10.1 VISIT SCHEDULE

It is preferred that all study visits take place in the morning when fasting blood samples are required.

The study visits occur on the planned dates (relative to the first injection), as scheduled. The visit schedule should be adhered to within the ± 2 day visit window.

If a patient is prematurely discontinued from treatment, all assessments planned at the End of Treatment visit should be performed.

Prior to all screening assessments, after discussion of participation in the study, the written consent form (including voluntary participation in pharmacogenetic testing and for future use of samples) must be signed and dated.

[figure not shown]
Although the screening assessments for this study are grouped under the heading of a single visit in this protocol, it is possible for them to be performed over more than 1 site visit if necessary, as long as the screening visit window prior to Day 1 is respected. Patients that fail screening for exclusion criteria, e.g. concomitant medications, required drug-specific discontinuation periods or laboratory tests, may be rescreened for study eligibility 1 additional time (refer to [Section 8.4](#) for further instructions related to rescreening).

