Cases of overdose are reported in the AE e-CRF pages as AESI if symptomatic or AE if asymptomatic. The reported cases of overdose will be described in the AE analysis (see [Section 2.1.4](#) and [Section 2.4.5.1](#)).

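### The dosing window, read as worded, permits injections 3 or 4 days apart that also meet the overdose definition, and the SAP applies the window from a different anchor

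*Protocol*

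**What the plan says.** Protocol 8.1 sets the dosing window: "The IMP is administered every 7 days +/- 2 days from initial IMP administration". It adds: "This is permitted per protocol to accommodate special circumstances, eg. laboratory results pending, ongoing AE, patient scheduling difficulty". After a missed or interrupted dose the calendar is not reset: "If IMP administration is missed or temporarily discontinued, the initial schedule of injections should be resumed". Protocol 10.1 ties visits, at which study drug is also given, to the same origin: "The study visits occur on the planned dates (relative to the first injection), as scheduled", again with 2 days either side.

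Protocol 10.4.1.3 describes overdose as something the investigator suspects or the patient volunteers, "defined as at least twice the intended dose during an interval of less than 5 days". A symptomatic overdose is an AESI, notifiable within 24 hours (Protocol 10.4.5 and Table 2). Otherwise, "asymptomatic overdose has to be reported as a standard AE". The SAP repeats the split in 2.4.3.2: "Cases of overdose are reported in the AE e-CRF pages as AESI if symptomatic or AE if asymptomatic".

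The same SAP section cites the protocol's weekly schedule with 2 days' tolerance, but applies it to the time between one injection and the next. Fewer than 5 days counts as an advanced injection and more than 9 days as a delayed one.

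**The concern.** A window around fixed calendar dates and a window around the previous dose allow different gaps. On the calendar reading, a late dose followed by an early one can bring two injections within the overdose interval while each is on protocol. A site then has two passages to follow: one says the dosing is permitted, and the other says it meets the definition of a reportable event.

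What is at stake is the consistency of overdose AE and symptomatic-overdose AESI counts across sites, and the meaning of the SAP's advanced and delayed injection counts. No efficacy endpoint is involved.

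**Working it through.** **Inputs.** Nominal interval 7 days, tolerance 2 days either side, anchor at the first dose (Protocol 8.1). Overdose cutoff: less than 5 days (Protocol 10.4.1.3). Advanced and delayed cutoffs: under 5 and over 9 days (SAP 2.4.3.2). Weekly-arm dose: "one injection of SAR156597 200 mg administered subcutaneously every week".

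**Step 1: reproduce the 5-day cutoff.** If the window runs from the previous dose, the gap is 7 + e, with e from -2 to +2. The minimum is 7 - 2 = 5 and the maximum is 7 + 2 = 9. These are the SAP's two cutoffs, and the lower one matches the overdose cutoff. No permitted gap is under 5 days, so there is no conflict on this reading.

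**Step 2: apply Protocol 8.1 as worded.** Dose k is planned 7k days after the first dose and given with offset e(k) from -2 to +2. The gap between consecutive doses is 7 + e(k+1) - e(k).
- Minimum: 7 - 2 - 2 = 3 days. Maximum: 7 + 2 + 2 = 11 days.
- Example: doses planned for days 7 and 14 after the first dose, given on days 9 and 12. Both are in window and 3 days apart.

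In whole days there are 5 × 5 = 25 offset pairs:

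| Gap (days) | 3 | 4 | 5 | 6 | 7 | 8 | 9 | 10 | 11 |
|---|---|---|---|---|---|---|---|---|---|
| Pairs | 1 | 2 | 3 | 4 | 5 | 4 | 3 | 2 | 1 |

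Three pairs fall under 5 days: (+2, -2) gives 3 days; (+2, -1) and (+1, -2) give 4 days. Three pairs exceed 9 days. The SAP would label the first group advanced and the second delayed, although every dose is in window. The gap from the first dose to the second cannot be under 5 days, because the first dose is the anchor.

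**Step 3: compare with the overdose definition.** In the weekly arm, two injections are 2 × 200 = 400 mg, twice the single dose. A 3-day gap qualifies however days are counted. A 4-day gap qualifies on elapsed days, but counted inclusively it spans 5 calendar days and does not.

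**Step 4: arms.** In the every-2-weeks arm adjacent injections are active and placebo, so active doses are at least 14 - 4 = 10 days apart. The placebo arm has no active doses. Two active doses under 5 days apart are therefore possible only in the weekly arm.

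**Step 5: frequency.** The documents give no offset data, so what follows is assumption. With independent offsets, the probability that a pair is under 5 days apart is P(+2)P(-2) + P(+2)P(-1) + P(+1)P(-2).
- Delays only (offsets 0 to +2): the minimum gap is 7 + 0 - 2 = 5, so the rate is 0.
- 80% on the day, 8% at each of ±1, 2% at each of ±2: 0.0004 + 2 × 0.0016 = 0.0036.
- 60%, 15% each, 5% each: 0.0025 + 2 × 0.0075 = 0.0175.

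Counting 3/25 = 12% as a rate would require all offsets to be equally likely, which nothing supports.

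**The case against.** The strongest reply is that the window was meant dose to dose. The SAP applies it that way, and the 5-day overdose cutoff begins exactly where such a window ends. On that view the reference to the initial administration only says when weekly dosing starts. This is a fair account of what may have been intended, and it shows that the anchor is ambiguous across the documents. It does not remove the problem: the instruction to resume the initial schedule and the visit rule both point to the first-dose calendar, and sites dose from the protocol, not the SAP.

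Three further objections stand and limit the point.
- A reader might infer that every in-window short gap will be reported as an overdose, or that any symptom then makes it an AESI. The definition depends on suspicion or notification, and the AESI is a symptomatic overdose; a coincidental symptom does not clearly qualify.
- A reader might infer that a true double dose would be hidden. Administration dates are recorded in the e-CRF and the SAP counts advanced injections separately, so the dates distinguish a same-day double dose from a 3-day gap.
- The window is offered for special circumstances. Two of the protocol's examples, pending laboratory results and an ongoing AE, naturally cause delay, while every short gap needs the second dose to be early.

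**Conclusion.** The conflict holds on the wording of Protocol 8.1 and 10.4.1.3. Permitted gaps run from 3 to 11 days, the 3-day gap meets the overdose definition without qualification, and the 4-day gap meets it on elapsed days. The SAP's dose-to-dose use of the window, 5 to 9 days, does not match that anchor. This conclusion needs no assumption about how often such gaps occur.

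The practical effect is narrower: sites may differ in whether they report a short in-window gap. Under blinding that question arises in all three arms, although only the weekly arm can receive two active doses so close together.

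It is tempting to multiply the assumed pair rates over a year of weekly dosing and conclude that a large share of patients would have an overdose event. The documents do not support that: the result depends entirely on assumed independent, symmetric offsets and falls to zero if deviations are only delays. Safety analyses are essentially descriptive, so the matter is one of clean safety reporting.

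**What to change.** Reconcile Protocol 8.1, Protocol 10.4.1.3 and SAP 2.4.3.2 (both its advanced/delayed injection cutoffs and its overdose reporting sentence) so that the window has the same anchor throughout and no dosing interval permitted by it also meets the overdose definition. State how days are counted. Tell sites how doses already given are to be classified. Which anchor or interval is right is for the sponsor to decide; none is proposed here.

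The cost is one protocol clarification, matching wording in the SAP and a site memo. No new data are needed, because injection dates are already collected.
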